1. SUMMARY

Although there is no evidence of teratogenicity from reproductive toxicology studies of Twinrix, GlaxoSmithKline (GSK) will manage this registry as part of an ongoing program of safety monitoring. Women judged to be at risk of hepatitis A and hepatitis B may be exposed to Twinrix before or during pregnancy. This registry is considered essential because of the potential for exposure during pregnancy and the unknown risks to pregnancy of any new chemical entity.

The purpose of the registry is to detect potential evidence of teratogenicity associated with prenatal use of Twinrix, if such teratogenicity exists, by collecting and analyzing voluntary (spontaneous), prospective reports of Twinrix prenatal exposures. Twinrix is designated as FDA Pregnancy Category C, which means that its safety in human pregnancy has not been determined. Registry statistics can supplement animal reproductive toxicology studies and assist clinicians in evaluating the potential risks and benefits of vaccination for individual patients. Registries do not collect control data from a comparison group, but proportions of birth defects in Twinrix-exposed pregnancies could be compared to the proportions of birth defects reported in the medical literature. A major limitation of an exposure-registration study is that the pregnancies that are reported may not be representative of all vaccinated pregnancies. Because reports of exposure are voluntary, they are subject to multiple biases.

Each registry report will contain a description of all prenatal exposures to Twinrix that are reported to GSK. Greater emphasis is placed upon pregnancies which are prospectively reported. Prospectively reported exposures are those reported while the pregnancy is ongoing; i.e., before the outcome is known. Because the outcome of the pregnancy is unknown when the prenatal exposure is reported, follow-up to determine the pregnancy outcome is required. Prospective reporting of ongoing pregnancies prior to knowledge of the pregnancy outcome reduces bias and permits estimation of the risk of birth defects.

The risk of pregnancy loss (also called miscarriage, spontaneous abortion, and intra-uterine fetal demise) is high early in gestation and decreases substantially from week 8 to week 28, yielding a cumulative estimated risk of 10-22% [Anderson, 2000, Fenster, 1997, Khattak, 1999, Osborn, 2000, Ventura, 2000, Wilcox, 1981, Wilcox, 1983, Wilcox, 1988, and Windham, 1997]. Although GSK will carefully review each pregnancy outcome, calculation of risk of spontaneous abortion should not be attempted and cannot be compared to background risk because pregnancies in this registry are reported at variable and, occasionally, imprecise times. Furthermore, pregnancy losses occurring early in gestation may not be recognized and/or reported. For example, if a pregnancy were recognized at 10 weeks of gestation and reported to the Registry, only a spontaneous abortion that was reported to the registry after this time would be available for analysis.

Retrospective reports, in which the pregnancy outcomes are known at the time of reporting, will also be reviewed. Retrospective reports are likely to be biased toward the reporting of more unusual and unfavorable outcomes and are less likely to be representative of the general population [Mitchell, 1988 and Wilcox 1984]. Therefore, the inclusion of such reports for calculation of probability (risk) of birth defects is

inappropriate. The purpose of summarizing the retrospective reports is to assist in the detection of any unusual patterns that may exist among the reported birth defects.

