3.5. Analysis

Pregnancy outcomes will be stratified by the trimester of exposure, with an additional stratum for preconception exposure with no subsequent administration during pregnancy. Reports of multiple exposures (i.e., multiple administrations of Twinrix) during a pregnancy will be classified by the earliest trimester of exposure. When exposure occurs before and after conception, the exposure will be classified by the dose administered after conception. Gestational weeks will be counted from the date of the last menstrual period. The second trimester will be considered to begin at week 14, and the third trimester beginning at week 28.

The calculations of risk for birth defects will be made by dividing the number of infants with birth defects by the total number of infants with and without birth defects. Spontaneous abortions and induced abortions not including birth defects will be excluded from this calculation. An exact 95% confidence interval (CI) will be calculated using the software application Stata, version 8.2 (Stata Corporation, College Park, TX).

The risk in the general population of all birth defects meeting CDC criteria is approximately 3% (range 2%-5%) of live births [Centers for Disease Control]. The estimated risk cited in medical literature varies because of differences in case definitions, populations sampled, and ascertainment methods. The Collaborative Prenatal Project, using a broader case definition and prospective ascertainment, reported a frequency of 5-7% [Chung, 1975]. Most major structural defects originate during the first trimester of pregnancy, which is the critical time for organogenesis. For such defects, exposures occurring in the second or third trimester are not likely to be causally associated. However, for the sake of completeness, and to enable the

CONFIDENTIAL

assessment of possible increases in the frequency of birth defects, all defects will be included in the reports for this Registry.

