Criteria for review of a specific individual report include: 1) was the timing of the exposure to Twinrix commensurate with the ontogenetic development of the organ(s) affected by the abnormalities; 2) was there another known or likely cause (e.g., preexisting genetic or chromosomal defect or exposure to a known teratogen); 3) was the congenital abnormality not previously described (i.e., was it new to medical science); 4) was there a unique constellation of defects (i.e., was there a new syndrome)? Criteria for review of aggregate data include: 1) was there a deviation from the expected frequency of all defects indicating an increase in the overall risk of defects; 2) was there a deviation from the expected frequencies of individual defects; 3) was there uniqueness (e.g., a pattern) of the abnormalities that is suggestive of a common etiology? Studies have shown the risk of spontaneous abortion is high early in pregnancy and decreases substantially from week 8 to week 28, yielding a cumulative estimated risk of 10-22% [Anderson, 2000, Fenster, 1997, Khattak, 1999, Osborn, 2000, Ventura, 2000, Wilcox, 1981, Wilcox, 1983, Wilcox, 1988, and Windham, 1997]. Calculation of risk of spontaneous pregnancy losses overall should not be attempted and cannot be compared to the incidence in the general population because pregnancies in this Registry are reported at variable and, occasionally, imprecise times. Also, pregnancy losses occurring early in gestation may not be recognized and/or reported.

While the Registry is limited to prospective reports, some pregnancy exposures are reported only following pregnancy outcome (retrospective reports). The Registry will also review each retrospective report involving a birth defect. In general, retrospective notification of outcomes following exposures to drugs or vaccines is biased toward reporting the severe and unusual cases, and is not reflective of the general experience with the drug. Moreover, information about the total number of exposed persons is unknown. Therefore, incidences of outcomes cannot be calculated from these data. However, a series of reported birth defects can be analyzed to detect patterns of specific congenital abnormalities and can identify early signals of new vaccine-associated risks. A separate section of each registry report will describe all abnormal outcomes of retrospectively reported cases.

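### Literature rates are the only named comparator, and the trimester strata the plan already forms are never contrasted, so an excess cannot be separated from definition or reporting differences

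*Combined protocol and SAP*

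**What the plan says.** The Summary says that "Registries do not collect control data from a comparison group" and that "proportions of birth defects in Twinrix-exposed pregnancies could be compared to the proportions of birth defects reported in the medical literature". No other comparator is named anywhere in the plan.

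Section 3.5 gives two literature figures. The first is "The risk in the general population of all birth defects meeting CDC criteria is approximately 3% (range 2%-5%) of live births". The second comes from a perinatal project which, "using a broader case definition and prospective ascertainment, reported a frequency of 5-7" per cent. The section also says that the literature estimate "varies because of differences in case definitions, populations sampled, and ascertainment methods". It does not say which figure is the registry's expected rate. Section 3.3 sets a registry definition wider than CDC's: minor defects count, and conditions off the CDC list may count.

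On strata, section 3.5 says "Pregnancy outcomes will be stratified by the trimester of exposure, with an additional stratum for preconception exposure with no subsequent administration during pregnancy". After noting that most major structural defects arise in the first trimester, it adds: "For such defects, exposures occurring in the second or third trimester are not likely to be causally associated". Later-exposure data are kept for completeness and also to allow possible increases in frequency to be assessed. The only interval described is an exact 95% CI, stated directly after the formula for a single risk. The first aggregate criterion asks: "was there a deviation from the expected frequency of all defects indicating an increase in the overall risk of defects". The second and third ask about individual defects and about patterns.

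**The concern.** The stated purpose in section 2 is to detect any major teratogenic effect. Judged against literature alone, a raised proportion has at least three explanations: the vaccine, the wider case definition (3.3), and selective reporting, since 3.7 says high-risk pregnancies may be reported more often. The plan acknowledges the last two but includes no analysis that would help tell them from the first.

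The later-exposed strata could help. They share the case definition, the voluntary prospective reporting and the follow-up contact in the month of expected delivery, and the plan itself supplies the reason why they are close to unexposed for most major structural defects. Without a prespecified contrast, readers of each annual report will compare the strata informally, with no interval and no rule for interpretation.

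**Working it through.** The documents give no sample size, power, detectable risk or signal threshold, so there is no figure of the plan's to reproduce. What follows is illustration. Group sizes and true risks are assumptions; the benchmarks 3%, 5%, 6% and 7% lie within the ranges cited in 3.5.

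**1. How far the answer depends on the literature rate chosen.** For n infants and benchmark p0, let r be the smallest count with P(X ≥ r | n, p0) ≤ 0.025. The lower limit of the exact 95% CI then exceeds p0 when X ≥ r, and the chance of this at true risk p is P(X ≥ r | n, p).

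No vaccine effect, true registry rate 6% (inside the cited 5-7%), n = 200:

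| Benchmark p0 | r | P(CI wholly above p0) |
|---|---|---|
| 3% | 12 | 0.54 |
| 5% | 17 | 0.095 |
| 6% | 20 | 0.018 |

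Against 3%, the probability at n = 200 is 0.30, 0.54 and 0.75 for true rates of 5%, 6% and 7%. At n = 300 and a true 6% it is 0.72.

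The reverse error is also possible. If the registry's background is really 3% and exposure doubles it to 6%, the CI clears a 5% benchmark with probability 0.04 (n = 100) to 0.15 (n = 500), and a 7% benchmark with probability below 0.01.

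**2. What an internal contrast can show.** Two-sided Fisher exact test at 0.05, first-trimester v later-only infants; the probability is that of a significant excess in the first-trimester group:

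| Sizes | True risks | Probability |
|---|---|---|
| 200 v 100 | 6% v 6% | 0.016 |
| 200 v 100 | 12% v 6% | 0.34 |
| 200 v 100 | 18% v 6% | 0.84 |
| 200 v 30 | 12% v 6% | 0.06 |

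For comparison, 200 first-trimester infants at a true 12% against a fixed and correct 6% give 0.84 (r = 20).

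**3. Sizes for 80% power to detect a doubling** (two-sided 0.05, normal approximation): 356 + 356 infants on a 6% background, 749 + 749 on 3%. A one-sample comparison with a correct fixed rate needs about 152 and 318. The internal contrast thus needs about 2.3 times as many first-trimester infants (356/152 = 2.34; 749/318 = 2.36), plus the later group.

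**4. Whether the strata are alike.** Section 3.5 leaves out of the risk only those abortions without defects, so abortions with defects count. A woman first exposed in the second or third trimester can enter only after surviving early losses and terminations. First-trimester registrants can therefore contribute defect-affected early losses that later registrants cannot, which may raise the ratio with no vaccine effect. Among births the asymmetry is smaller, because every infant born has passed the early period whichever group it belongs to. The 0.016 in step 2 assumes equal true risks and does not cover this bias.

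**The case against.** The strongest case against has four parts.

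- **Most of step 1 is a failure to choose a benchmark.** This largely stands. The 0.54 and 0.72 arise only when a broad-definition registry is held to the CDC 3%. Naming the 5-7% figure removes much of that problem, but not selective reporting, which no literature rate shares.
- **The internal contrast is imprecise.** This stands. A reader might infer that literature is simply the weaker benchmark. The figures do not support that: it is weaker in comparability but stronger in precision (0.84 against 0.34 for 12% v 6%). The documents give no stratum sizes, so even 100 later-exposed infants is an assumption.
- **The strata are not exchangeable.** This stands, and showing gestational week at registration would not by itself correct it. Nor are the later strata a reference for every defect: the plan's causal statement covers most major structural defects, while the registry also counts minor and chromosomal ones.
- **The plan already uses timing.** Stratified outcomes will be visible, individual review asks whether exposure timing fits the organ affected, and aggregate criteria 2 and 3 look beyond overall risk. It would be wrong to infer that the plan ignores trimester or keeps later exposures merely for completeness. What is missing is a stated contrast with an interval and a rule for reading it.

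A reader might also infer that the Summary's statement about comparison data is false. It is not: every registrant is exposed, and no unexposed control group is collected.

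**Conclusion.** The concern holds in a limited form. The plan names only an external comparator, cites rates spanning 2% to 7% without choosing one, uses a definition wider than the lower of them, and specifies no contrast between strata that it already forms. An excess over literature therefore cannot be separated from definition or reporting differences. In the illustration, the chance of an apparent excess with no vaccine effect runs from 0.018 to 0.54 according to the benchmark used (n = 200, true rate 6%, both assumed).

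The internal contrast is a supplement to the literature comparison. Its usefulness rests on enough later-exposed pregnancies being registered, and on the later group being a fair reference for structural defects once abortions with defects are set aside.

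**What to change.** In section 3.5, prespecify one supportive contrast for each registry report:

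- the risk ratio and risk difference, with exact 95% CI, for first-trimester exposure versus pregnancies whose only exposure was in the second or third trimester;
- preconception-only exposure kept as its own row;
- structural defects shown separately from all defects;
- gestational week at registration shown for both groups;
- the contrast repeated in births only (live births and stillbirths, leaving out abortions with defects), so that both groups have a similar opportunity to contribute defects.

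Read the first aggregate criterion on this contrast beside a literature rate matched to the registry's broader definition, which among the cited figures is 5-7% and not the CDC 3%. Keep the Summary's statement that no control group is collected, and add that later-exposed pregnancies serve as a supportive internal reference. State in each report that only large effects can be shown and that a null result is not reassurance.

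The cost is one added table from data the registry already collects, with no new patients or procedures. The downside is a wide interval if the later group is small.

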3. METHODS

3.1. Registration and Follow-up

Reporting of exposed pregnancies is voluntary. Pregnancies will be registered following maternal exposure to Twinrix within 28 days prior to conception or during pregnancy. Registration of pregnancies is prospective, i.e., reported during pregnancy before the pregnancy outcome is known. Retrospective reports, i.e., those for which the outcome is known at the time of registration, will also be reviewed. However, because retrospective reports are more likely to be biased by relatively more frequent reporting of abnormal outcomes, such reports are less likely to be representative of the general population experience and, therefore, cannot be used for risk assessment or analysis [Mitchell, 1988 and Wilcox, 1984]. Health care providers with patients exposed to Twinrix during pregnancy will be encouraged to enroll their patients in the Registry as early in the pregnancy as possible to maximize the validity of the study. Health care providers can enrol their patients by calling the telephone number PPD [REDACTED].

When the pregnancy is reported prospectively, the Registry will collect registration data from the reporter through telephone interview or a short registration form. In the

CONFIDENTIAL

month of the estimated date of delivery follow-up will be sought by telephone contact or a form mailed to the health professional. Information about maternal events throughout the pregnancy, pregnancy outcome, and neonatal health is requested. Additional follow-up is not sought from subsequent health care providers.

A report of an exposure will be closed when clear information is received about exposure to Twinrix and pregnancy outcome determination, or when the patient is lost to follow-up. A patient is considered to be lost to follow-up when the Registry does not receive the minimum information, or if the reporting health care provider can no longer locate the patient. Only data from “closed” reports of exposed pregnancies with known outcomes will be considered for analysis.

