3.2. Inclusion criteria

For a pregnancy report to be considered eligible for registration, certain data must be available. The required data include:

- Documentation that Twinrix was administered \leq 28 days before or during pregnancy;
- Confirmation that the pregnancy is being prospectively reported;
- Report made by a patient or a health care professional;
- The timing of the prenatal exposure to Twinrix (no broader than during which trimester);
- A patient identifier that will allow follow-up to be obtained so that the pregnancy outcome can be ascertained;
- Whether the patient was involved in a clinical trial at the time of the exposure;
- Full reporter contact information.

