3.3. Classification of Outcomes

This Registry uses the term "birth defects" for outcomes sometimes referred to as “congenital anomalies.” For purposes of analysis, pregnancy outcomes will be dichotomized according to the presence or absence of birth defects. The latter group will be further categorized as: 1) Live births, 2) spontaneous abortions (i.e., pregnancy losses), and 3) induced abortions. This Registry has adopted a definition of a child with a birth defect as any live or stillborn neonate with a structural or chromosomal abnormality diagnosed before 6 years of age. The Registry will employ a conservative approach of including all defects, including minor ones, as congenital abnormalities. Therefore, conditions not appearing in the Centers for Disease Control and Prevention (CDC) Inclusion List may be classified as congenital abnormalities. All defects will be included in the “congenital abnormalities” category, regardless of whether or not the neonate is delivered alive, including structural defects in neonates delivered prior to 20 weeks of gestation or weighing less than 500 grams. However, CDC guidelines

disqualify as defects those findings that are present in infants delivered at less than 36 weeks of gestation and are attributable to prematurity itself, such as a patent ductus arteriosus or inguinal hernias. Infants with infectious conditions (e.g., neonatal sepsis) or biochemical abnormalities (e.g., hyperbilirubinemia) will be classified as being without congenital abnormalities unless there is a possibility that the condition reflects an unrecognized birth defect.

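### On its natural reading, the plan lets reports made after a prenatal test has shown a defect into the risk estimate, without requiring that knowledge to be recorded or planning an analysis that separates such reports

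*Combined protocol and SAP*

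**What the plan says.** Section 1 sets the criterion: "Prospectively reported exposures are those reported while the pregnancy is ongoing; i.e., before the outcome is known". Section 3.1 repeats it: "Registration of pregnancies is prospective, i.e., reported during pregnancy before the pregnancy outcome is known". Section 1 gives the reason: "Prospective reporting of ongoing pregnancies prior to knowledge of the pregnancy outcome reduces bias and permits estimation of the risk of birth defects". Reports with a known outcome are kept out of the risk calculation because, in the words of section 1, "Retrospective reports are likely to be biased toward the reporting of more unusual and unfavorable outcomes".

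Registration data are taken "through telephone interview or a short registration form". Among the seven required items in section 3.2, the only one on this subject is "Confirmation that the pregnancy is being prospectively reported"; none asks about prenatal tests or fetal findings. The registration form itself is not in the documents.

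Section 3.4 excludes retrospective reports only. Section 3.5 divides infants with defects by all infants with and without defects, gives an exact 95% CI, and plans one stratification: "Pregnancy outcomes will be stratified by the trimester of exposure", plus a preconception stratum. Section 3.7 concedes that prospective reports may be selective and offers high-risk pregnancies as an example. It names neither prenatal testing nor an analysis. The 2013 addendum deals with enrolment routes only.

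**The concern.** The protection offered by prospective reporting is that the reporter does not yet know how the pregnancy will turn out. Once a scan or test has shown a defect, that protection is weakened even though the pregnancy continues. If such pregnancies are reported preferentially, the observed risk rises with no vaccine effect; if they are reported less often, it falls.

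This matters because a deviation from the expected frequency of all defects is one of the aggregate review criteria in section 3.5. Sections 1 and 3.5 both say that reports arrive at variable times, so registration after testing is foreseeable. When an annual review shows a raised or reassuring figure, the reader needs some means of judging whether prior knowledge of the fetus contributed to it.

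**Working it through.** **Reading the text.** Four places bear on what counts as the outcome.

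- Sections 1 and 3.1 tie prospective status to an ongoing pregnancy whose outcome is unknown.
- Section 3.5 describes retrospective exposures as those reported only once the pregnancy outcome has occurred.
- Section 3.7 speaks of anomalies found at the time of the outcome.
- Section 3.3 lists live births, spontaneous abortions and induced abortions, and defines a child with a birth defect as "any live or stillborn neonate with a structural or chromosomal abnormality".

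Together these point to the end of pregnancy. Against that, section 3.3 also sorts outcomes by presence or absence of birth defects, so a defect seen on a scan could be argued to be a known outcome. No section settles it. Under the first reading, the report counts once it is closed with a known outcome (section 3.1) that confirms the defect.

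**Size.** The plan states no sample size or bias figure to reproduce. Only the baselines come from section 3.5: about 3% (range 2%-5%), and 5-7% under a broader case definition. Everything else is assumed:

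- no vaccine effect;
- share registered after testing, L = 0.4;
- share of defects visible by then, d = 0.3;
- relative reporting of known-defect pregnancies, k;
- relative reporting of late pregnancies with no visible defect, m.

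For baseline b:

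- defect weight D = b × {(1−L) + L × [(1−d)m + dk]}
- no-defect weight N = (1−b) × {(1−L) + Lm}
- registry risk = D/(D+N)

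At b = 3%:

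| k | m | Registry risk |
|---|---|---|
| 1 | 1 | 3.00% |
| 2 | 1 | 3.35% |
| 3 | 1 | 3.69% |
| 5 | 1 | 4.38% |
| 0.5 | 1 | 2.83% |
| 2 | 2 | 3.00% |
| 3 | 2 | 3.25% |

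Worked line, k = 3, m = 1: the multiplier is 0.6 + 0.4 × (0.7 + 0.9) = 1.24, so 0.0372/(0.0372 + 0.97) = 3.69%.

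Worked line, k = 3, m = 2: D = 0.03 × [0.6 + 0.4 × (1.4 + 0.9)] = 0.0456 and N = 0.97 × 1.4 = 1.358, giving 3.25%.

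With L from 0.2 to 0.6, d from 0.2 to 0.4 and m = 1, k of 2 to 5 gives 3.1%-5.7%, and k = 0.5 gives 2.6%-2.9%. The registry also counts minor defects. At b = 6%, k = 3 and m = 1 give 7.3%.

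**Effect on a signal.** At a true 3.69%, the chance that the exact lower limit exceeds 3% is 3%, 7% and 12% with 100, 200 and 500 infants, against 1%, 2% and 2% at a true 3.00%. The chance that it exceeds 5% is about 0.1% or less.

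**Dropping known-defect reports only.** Setting k = 0 and m = 1 gives a multiplier of 0.88, and 0.0264/(0.0264 + 0.97) = 2.65%. That remedy would bias the risk downward.

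**Splitting by knowledge at registration.** With k = 3 and m = 1, pregnancies registered before testing show 3.0%. Those registered after it have multiplier 0.7 + 0.9 = 1.6, so 0.048/(0.048 + 0.97) = 4.7%. With 120 and 80 infants, the observed order is tied or reversed about 30% of the time, and Fisher's exact test is significant at 5% in about 7%.

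**The case against.** The strongest reply is that the plan nowhere says such a report is prospective. A reader might infer that the plan knowingly admits these reports; the documents do not support that. They are silent, and the presence-or-absence wording in section 3.3 lets a prenatally seen defect be treated as a known outcome. This stands, and it is why the point rests on the most natural reading. It does not remove the point: excluding only known-defect reports would bias the risk downward instead, so either reading needs a written rule.

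A second reply is disclosure. Section 3.7 admits selective prospective reporting, section 1 warns of multiple biases, section 3.1 urges early enrolment, and section 2 describes an early-signal registry. All of that is fair, but none of it separates the reports in question.

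A reader might also infer that the bias cannot be examined at all. That goes too far. Section 3.1 times follow-up by the estimated delivery date, so a crude split by gestational age at registration may be derivable, and the unseen registration form may ask about prenatal results.

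Finally, the size is assumed and its direction uncertain. That stands in full: extra reporting after tests that show no defect offsets the inflation, completely when k = m = 2.

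**Conclusion.** The point holds as a gap in the required data and the planned analysis. On the natural reading, reports made after a visible defect enter the risk estimate and can carry the bias for which known-outcome reports are excluded, with no planned analysis to show it.

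The likely effect is modest and may go either way: roughly 2.8% to 3.7% around a 3% baseline under the central assumptions, for half-rate to threefold reporting of known defects. A reader might infer that the registry's risk is inflated. The documents do not support that, since they give no figure for late registration, prenatal detection or relative reporting.

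This is a cheap improvement that should be made, held with medium confidence; it does not invalidate the main estimate.

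**What to change.** - **Section 3.1:** state that a report made after a prenatal finding in an ongoing pregnancy stays prospective and is flagged.
- **Section 3.2:** add the item *prenatal test or scan results on the fetus known at registration: none / normal / abnormal*.
- **Section 3.5:** keep the all-prospective estimate as the main one. Beside it, with its exact CI, show a sensitivity estimate limited to pregnancies registered before any fetal result, normal or abnormal, was known. Present it descriptively, with no rule that discounts signals.
- **Pregnancies already registered:** use gestational age at registration, where derivable, for a crude early/late split.

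The cost is one more question and one more table row; the main estimate and signal review are unchanged. The limits should be stated with the result:

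- The CI is wider. At 3%, mean exact width is about 5.2 points with 200 infants and 6.9 with 120 (6.9/5.2 ≈ 1.3), if 60% are retained, which is an assumption.
- It says little about second- and third-trimester exposures, few of which can be registered before any fetal result is known.
- Power to show a difference is low, as calculated above.
- Later registrants have already passed early losses and terminations, so a difference between the groups would not by itself prove selective reporting.
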